8.1. Data Quality Assurance

To ensure accurate, complete, and reliable data, Lilly or its representatives will do the following:

- provide instructional material to the study sites, as appropriate
- sponsor start-up training to instruct the investigators and study coordinators. This session will give instruction on the protocol, the completion of the CRFs, and study procedures
- make periodic visits to the study site
- be available for consultation and stay in contact with the study site personnel by mail, telephone, and/or fax
- Review and evaluate eCRF data and/or use standard computer edits to detect errors in data collection.
- Conduct a periodic review of the database.

In addition, Lilly or its representatives may periodically check a sample of the patient data recorded against source documents at the study site. The study may be audited by Lilly and/or regulatory agencies at any time.

The investigator will keep records of all original source data. This might include laboratory tests, medical records, and clinical notes. If requested, the investigator will provide the sponsor, applicable regulatory agencies, and applicable IRB/ERBs with direct access to the original source documents.

8.2. Data Capture Systems

8.2.1. Case Report Form

An electronic data capture system will be used in this study. The site maintains a separate source for the data entered by the site into the sponsor-provided, electronic data capture system.

Any data for which paper documentation provided by the patient will serve as the source document will be identified and documented by each site in that site's study file. Paper documentation provided by the patient may include, for example, a paper diary to collect patient-reported outcome measures, a daily dosing schedule or an event diary.

For data handled by a data management third party organization (TPO), CRF data and some or all data that are related will be managed and stored electronically in the TPO system.

Subsequent to the final database lock, validated data will be transferred to Lilly's data warehouse, using standard Lilly file transfer processes.

For data handled by Lilly internally, CRF data and some or all data that are related will be managed by Lilly and stored electronically in the Lilly's system.

8.2.2. Ancillary Data

Data managed by a central vendor will be stored electronically in the central laboratory's database system. Data will subsequently be transferred from the central vendor to the Lilly system and TPO system.

Bioanalytical data will be stored electronically in the bioanalytical laboratory's database. Data will subsequently be transferred from the bioanalytical laboratory to the Lilly system and TPO system.

Electrocardiogram data will be stored electronically in the central database system of Lilly's central review organization. Data will subsequently be transferred from the central review organization system to the Lilly system and TPO system.

9. Data Analyses

9.1. General Considerations

Patients will be enrolled in this multicenter, open-label, Phase 1 study with dose escalation [REDACTED] design followed by dose confirmation in 6 tumor-specific expansions. During dose escalation, patients were enrolled [REDACTED] the total number of patients in a specific cohort was determined based on the occurrence of DLTs at that dose level (refer to Section 6.2.2), [REDACTED] During dose confirmation, at least 15 and up to 45-60 patients will be enrolled in each of 6 tumor-specific cohort expansions (refer to Section 6.2.3).

Statistical analysis of this study will be the responsibility of Eli Lilly and Company.

The analyses for this study will be descriptive. Data analyses will be provided [REDACTED] for all study patients combined wherever appropriate. For continuous variables, summary statistics will include number of patients, mean, median, standard deviation, standard error, minimum, and maximum. Categorical endpoints will be summarized using number of patients, frequency, percentages, and their standard errors. For time to event endpoints, the Kaplan-Meier curves (Kaplan and Meier 1958) will be estimated. Quartiles and rates at various time points, together with the 95% CIs, will be provided. Missing data will not be imputed.

The interpretation of the study results will be the responsibility of the investigator with the Lilly CRP, pharmacokineticist, statistician and Associate Consultant for Clinical Trial Management. The Lilly CRP and statistician will also be responsible for the appropriate conduct of an internal review process for both the final study report and any study-related material to be authorized for publication by Lilly.

[REDACTED]

9.1.1. Determination of Sample Size (Parts B, C, D, E, F, and G)

Although at least [REDACTED] patients will be enrolled in each of the 6 tumor-specific expansions, up to 45-60 patients may be enrolled in each tumor-specific expansion if approved by the sponsor. The sample size of up to 45-60 patients for each of the 6 tumor-specific expansions is based on differentiating 34.5% to 40% from 5% (uninteresting) overall response rate (ORR) in tumors with (marker present) and without (marker absent) a tumor-relevant exploratory marker, respectively (that is, $ORR_{marker\ present}=34.5\%$ to 40% and $ORR_{marker\ absent}=5\%$). Examples of tumor-relevant exploratory markers include KRAS (non-small cell lung cancer, colorectal cancer), CDKN2A (glioblastoma multiforme, melanoma), and estrogen receptor (ER; breast cancer). Assuming an equal number of patients having tumors with and without the exploratory marker, 45 or 60 patients provide approximately 85% power to differentiate 40% or 34.5% from 5% ORR, respectively (refer to Table JPBA.9.1). To maximize the power to detect the ORR difference between the marker groups, enrollment to a tumor-specific expansion may be adjusted to achieve an equal number of patients having tumors with and without the exploratory marker.

9.1.2. Patient Disposition

All patients who discontinue from the study will be identified, and the extent of their participation in the study will be reported. If known, a reason for their discontinuation will be given.

9.1.3. Patient Characteristics

Patient characteristics will include a summary of the following:

- Patient demographics
- Baseline disease characteristics
- Prior disease-related therapies
- Concomitant medications

Other patient characteristics will be summarized as deemed appropriate.

9.1.4. Safety Analyses

Safety analyses will be conducted on all patients who have received at least 1 dose of the study drug.

All patients who receive at least 1 dose of LY2835219 will be evaluated for safety and toxicity. Adverse events will be classified using the CTCAE **CCI**

Safety analyses will include summaries of the following:

- AEs, including severity and possible relationship to study drug
- Dose adjustments
- DLTs
- Laboratory measures and electrocardiograms.

9.1.5. Pharmacokinetic Analyses

[figure not shown]
Pharmacokinetic (PK) analyses will be conducted on patients who have received at least 1 dose of the study drug and have sufficient samples collected to allow the estimation of LY2835219 PK parameters.

Pharmacokinetic (PK) parameter estimates for LY2835219 will be computed by standard noncompartmental methods of analysis using CCI Professional Edition on a computer that meets or exceeds the minimum requirements for this program. The maximum concentration (C_{max}), area under the concentration-time curve (AUC), half-life ($T_{1/2}$), volume of distribution (V_d), clearance (CL), and other relevant parameters that can be calculated from the data will be reported from the noncompartmental analyses.

Providing that the data allow, the PK parameter estimates (C_{max} and AUC) for LY2835219 will be evaluated statistically to delineate the effects of dose proportionality using the methods described previously (Smith et al. 2000). Least-squares estimates of geometric means and their corresponding 90% confidence intervals (CI) will be provided by dose, together with the dose-normalized ratio of geometric means and CI.

In addition, the plasma PK data of LY2835219 will also be analyzed using nonlinear mixed effect modeling CCI (Section 9.1.7). The version of any software used for the analysis will be documented and the program will meet Lilly requirements of software validation. It is possible that other validated equivalent PK software programs may be utilized if appropriate, warranted, and approved by Lilly Global PK management.

Finally, in Part G, the plasma concentration data of fulvestrant will also be analyzed by standard noncompartmental methods of analysis, and any relevant PK parameter that can be calculated from the data will be reported.

9.1.7. Pharmacokinetic/Pharmacodynamic Analyses

In addition to a standard noncompartmental assessment, the plasma concentration data of LY2835219 will also be analyzed by means of a compartmental approach using CCI. Plasma data from all patients will be pooled for analyses to determine the compartmental PK parameters and between- and within-patient variability. Covariates analysis will be also performed. Once a structural and statistical model has been established, the effect of patient factors will be assessed. Covariate data distributions will be assessed.

This population PK model will then be used to develop a PK/PD model where the levels of Rb, pRb and topoII α in hair follicles are the primary PD measure. Additional PK/PD models may be developed using other PD measures.

Since a secondary objective of this clinical trial is to determine a recommended dose range of LY2835219 that may be safely administered to patients with advanced cancer, the results from these analyses may be used to support dose selection for Phase 2 studies.

The PK/PD data will be analyzed using validated software programs (for example, CCI [REDACTED]). The version of the software used for the analysis will be documented and will meet the Lilly requirements of software validation.

9.2. Efficacy

Response and progression for tumors will be evaluated using the Response Evaluation Criteria in Solid Tumors (RECIST) Version 1.1 (Eisenhauer et al. 2009), with the notable exception that response and progression for lymphomas will be evaluated using the Revised Response Criteria for Malignant Lymphoma (Cheson et al. 2007).

Tumor response and time-to-event data will be tabulated. For each expansion cohort, the time-to-event data analysis will include calculation of 6-month progression-free survival probability. Any patient that discontinues due to a reason other than progressive disease or death (for example, AE, patient/investigator decision) will have their time-to-event data either censored at Visit 801 if no progressive disease is found during this visit, or censored at the date of the last objective progression-free disease assessment if progressive disease is found at Visit 801.

For Part G, patients may have already received 1 or more cycles of fulvestrant prior to study enrollment. This prior therapy confounds the interpretation of response and progression. As a result, tabulations of tumor response and time-to-event data will be considered descriptive only.

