Progression-Free Survival (PFS) time is defined as the time from the date of first day of study drug to the first date of progressive disease (symptomatic or objective) or death due to any cause, whichever occurs first. For patients who are not known to have died or progressed as of the data-inclusion cutoff date, PFS time will be censored at the date of the last objective progression-free disease assessment prior to the date of any subsequent anticancer therapy.

Overall Survival (OS) time is defined as the time from the date of first day of study drug to the date of death from any cause. For patients not known to have died as of the data cut-off date, OS time will be censored at the last contact date the patient was known to be alive prior to the cut-off date.

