### **6.3.9. Efficacy**

Efficacy assessments will be derived for patients during Dose Confirmation Phase (Parts B, C, D, E, F, and G).

Eastern Cooperative Oncology Group performance status (PS) will be listed and summarized for patients on therapy by cohort and cycle.

Reported lesion data (target or non-target) and investigator evaluation will be listed for patients on therapy.

Tumor markers will be listed for patients on therapy.

The best overall response, duration of overall response, duration of overall CR and duration of SD will be listed for patients on therapy. If appropriate, the efficacy endpoints, including Overall Response Rate, Disease Control Rate, Duration of Overall Response, Duration of

Overall CR, Duration of Stable Disease, PFS, and OS, will be summarized for Parts B, C, D, E F, and G.

The Overall Response Rate is defined as the proportion of patients who exhibits a confirmed CR or PR relative to baseline as defined by RECIST Version 1.1 (Eisenhauer et al. 2009). A responder is defined as any patient who exhibits a confirmed CR or PR relative to baseline assessment.

Disease Control Rate is defined as the proportion of patients in the analysis population who exhibit a SD or confirmed CR or PR relative to baseline during the study. Response is defined by RECIST Version 1.1 (Eisenhauer et al. 2009).

Overall Response Rate and Disease Control Rate with their respective 95% CI will be estimated using the Clopper-Pearson method. For time to event endpoints, including Duration of Overall Response, Duration of Overall CR, Duration of Stable Disease, PFS, and OS, the survival curve will be estimated by the Kaplan-Meier method (Kaplan and Meier 1958). Quartiles and rates at time points of every 3 months, together with the 95% CIs, will be provided.

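### Protocol 9.2 and SAP 6.1.2 define PFS differently for patients who stop for a reason other than progression or death, and the protocol version discards progressions found at Visit 801

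*Protocol*

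**What the plan says.** Protocol 9.2 asks for a 6-month PFS probability in each expansion cohort. It then sets a rule for anyone who discontinues for a reason other than progressive disease or death, such as an adverse event or a patient or investigator decision. Such patients "will have their time-to-event data either censored at Visit 801 if no progressive disease is found during this visit"; otherwise they are "censored at the date of the last objective progression-free disease assessment if progressive disease is found at Visit 801".

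SAP 6.1.2 measures PFS from first dose "to the first date of progressive disease (symptomatic or objective) or death due to any cause", whatever the reason for stopping. Censoring is reserved for those with neither event on record by the data cutoff; for this group the SAP says: "PFS time will be censored at the date of the last objective progression-free disease assessment prior to the date of any subsequent anticancer therapy".

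SAP 6.3.9 asks for Kaplan-Meier estimates and says: "Quartiles and rates at time points of every 3 months, together with the 95% CIs, will be provided". A 6-month PFS rate therefore comes out of the SAP as well.

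Protocol 7.1.2.2.3 and Table JPBA.7.1 put Visit 801 at 30 ±7 days after the last dose. Footnote g of Attachment 1 places radiology at baseline and then late in every other cycle from Cycle 2. In the extracted schedule, the follow-up column is marked for palpable and visible tumor measurement but not for radiology.

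**The concern.** The same patient can be an event in one document and censored in the other, so two analysts could report different 6-month PFS rates from one dataset.

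The protocol limb is also unsound taken alone. Its censoring date is chosen because progression was seen, which is outcome-dependent censoring and removes a known event from the curve.

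What is at stake is the accuracy of the reported cohort rates. No decision rule in the visible text uses PFS, and SAP 6.3.1 says the analyses are descriptive, without p-values.

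**Working it through.** The documents state no PFS rate, PFS power or rate of stopping for other reasons, so there is no plan figure to reproduce. The check compares the two rules, then sizes the gap on assumed inputs.

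**The rules side by side, for a patient who stops for a reason other than progression or death**

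| What happens next | Protocol 9.2 | SAP 6.1.2 | Result |
|---|---|---|---|
| Progression found at Visit 801 | Censored at last progression-free assessment | Event | Always conflict |
| No progression at Visit 801 | Censored at Visit 801 | Censored at last objective progression-free assessment before new therapy | Differ only if Visit 801 had no objective assessment or new therapy began first |
| Progression or death known after Visit 801, before cutoff | Censored, read literally | Event | Conflict, probably uncommon |
| Death after stopping, before Visit 801 | Not addressed | Event | Protocol silent |

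**Illustration (invented counts, 45 patients, Kaplan-Meier at day 182.6)**

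- 36 stay on schedule: progression in 11 at day 56, 8 at day 112 and 5 at day 168; 12 remain event-free past 6 months.
- 9 stop for other reasons after a clean day-56 scan. At Visit 801 (day 120), 5 have progression and 4 do not.
- Protocol (5 censored at day 56, 4 at day 120): 34/45 × 21/29 × 12/17 = 38.6%.
- SAP, no objective assessment in the 4 (5 events at day 120, 4 censored at day 56): 34/45 × 22/30 × 17/22 × 12/17 = 30.2%.
- SAP, objective assessment in the 4 (5 events, then 4 censored, at day 120): 34/45 × 26/34 × 21/26 × 12/17 = 32.9%.

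The gap is 38.6 − 30.2 = 8.4 points, or 38.6 − 32.9 = 5.7 points if Visit 801 is objective. Starting from 30.2%, the late censoring of clean patients alone raises the figure to 32.9%. Dropping the progressions alone raises it to 34/45 × 17/25 × 12/17 = 36.3%.

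**Simulation**

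Assumptions: exponential PFS, true 6-month PFS 30%, n = 45, Visit 801 at 30 days and clinical only, 2,000 replicates per setting. The stopping setting, the share of progressions found at Visit 801, and the hazard after stopping (unchanged or doubled) are varied. Entries are the mean of protocol minus SAP, in points, as unchanged / doubled hazard.

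| Stopping setting | None found | Half found | All found |
|---|---|---|---|
| 10% | 0.9 / 1.0 | 1.4 / 1.6 | 1.7 / 2.0 |
| 20% | 2.2 / 2.2 | 3.1 / 3.4 | 3.9 / 4.6 |
| 30% | 3.7 / 3.8 | 5.4 / 6.0 | 6.7 / 7.8 |

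Results at n = 60 agree within 0.1 point. The protocol estimate fell below the SAP estimate in at most 2.5% of replicates.

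The reverse is possible. Take 12, 8 and 6 scheduled progressions at days 56, 112 and 168, and 13 patients event-free. Add 6 stoppers with a clean day-112 scan and progression at Visit 801 on day 190. The protocol gives 33/45 × 25/33 × 13/19 = 38.0%; the SAP gives 33/45 × 25/33 × 19/25 = 42.2%, because those events fall after 6 months.

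**Error of each rule against PFS as the scan schedule would detect it (n = 45)**

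- Hazard unchanged: protocol +0.6 to +3.7 points; SAP −4.2 to 0.0.
- Hazard doubled after stopping: protocol +2.0 to +8.8; SAP −0.5 to +5.1.

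**The case against.** **Materiality.** PFS is secondary, SAP 6.3.9 summarizes it only if appropriate, and Part G is declared descriptive in Protocol 9.2. At 30% PFS and n = 45 the standard error is √(0.3 × 0.7/45) = 6.8 points, larger than most of the gaps above. This limits the importance of the point. It does not remove it: sampling error is noise, whereas this is a systematic difference on the same patients.

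**The SAP rule is not unbiased.** If Visit 801 is clinical only, a progression there counts but a clean visit adds no follow-up, so the estimate can read low. Under another set of assumptions (median PFS 8–24 weeks, 19–39% stopping independently of progression, everyone assessed), the SAP error with clean patients taken back to the prior scan was −1.3 to −4.5 points, against +0.7 to +2.5 for the protocol. This stands. The case for the SAP rule is that it keeps observed events and is already written, not that it is always nearer the truth.

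**Imaging may be done at discontinuation.** Protocol 7.3 and footnote h of Attachment 1 let repeat radiology be omitted when progression is otherwise evident, which suggests it may otherwise be obtained. That narrows the second row of the comparison but leaves the first untouched.

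**Some of the differences are minor.** Death before Visit 801 might be read as a contradiction, but the protocol is merely silent there and the SAP fills the gap. Progression after Visit 801 will seldom be known, because Protocol 7.1.2.2.3 normally ends participation then.

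**Scope.** A reader might infer that Protocol 9.2 overrides OS censoring, since it speaks of time-to-event data generally and SAP 6.3.9 uses the term broadly: "For time to event endpoints, including Duration of Overall Response, Duration of Overall CR, Duration of Stable Disease, PFS, and OS". The sentence follows directly on PFS and turns on finding progression, and the SAP has its own OS rule ("OS time will be censored at the last contact date the patient was known to be alive prior to the cut-off date"). The wording needs limiting, but an intent to change OS is not shown.

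**Withheld text.** Parts of the general statistical sections are blacked out, so a precedence statement there cannot be excluded.

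**Conclusion.** The conflict holds. It is certain from the text when progression is found at Visit 801, and conditional when none is found. The protocol rule usually gives the higher 6-month PFS, by roughly 1 to 8 points. That range rests on assumed stopping rates, detection shares and post-stopping hazards, and on a clinical-only Visit 801.

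A reader might infer that the two rules err in opposite directions. The documents do not establish that. It occurs when stopping is unrelated to progression and Visit 801 findings count asymmetrically; when stopping is informative, both rules can read high. Nor do the figures show that any replacement rule is more accurate than the SAP rule.

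This should be fixed, because a descriptive rate still needs one definition. The effect is confined to reported rates.

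**What to change.** - Delete the Visit 801 censoring sentence from Protocol 9.2 and use the SAP 6.1.2 PFS rule in both documents. Progression, or death from any cause, known by the cutoff is an event regardless of why the patient stopped. Otherwise censor at the last objective progression-free assessment before any subsequent anticancer therapy.
- State that Visit 801 serves as a censoring date only when an objective assessment was done there.
- State that OS and the response durations keep their SAP 6.1.2 definitions.
- Show the present Protocol 9.2 censoring as a sensitivity Kaplan-Meier run.
- Disclose that the change came after efficacy data had been transferred; Protocol 9.3.2 provides for transfers about every 3 months and/or at completion of each expansion, in an open-label study.
- Optionally, add a sensitivity run that censors events first documented after new anticancer therapy. This should not be part of the main rule.

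The cost is a protocol amendment removing one sentence, a few clarifying sentences in SAP 6.1.2, and one extra Kaplan-Meier run per expansion cohort (two with the optional run). No new visits or data are needed, since SAP 6.3.3.2 already lists post-treatment therapies.

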9.3. Interim Analyses

Although an external safety review committee will not be formed, safety data for all patients will be reviewed continuously throughout this study by Investigators, the Lilly CRP, and Lilly Global Patient Safety.

Only the assessment committee is authorized to review complete interim analyses. Study sites will receive information about interim results ONLY if they need to know for the safety of their patients or for dose escalation. The assessment committee may consist of the members of the study team.

